2.2.2 Secondary Efficacy Endpoints

Cycles of breastfeeding women will be excluded from the efficacy analyses but included in the analyses regarding safety and tolerability.

Secondary efficacy endpoints are:

- Pearl Index based on overall cycles (overall PI) in women aged ≤ 35 years
PI based on overall cycles will include all pregnancies which will occur during the trial in women aged ≤ 35 years (at the time of trial enrollment).
- PI for method failures in women aged ≤ 35 years
Method failures PI will include all pregnancies of women who used the IMP correctly. Pregnancies are to be excluded from the calculation if in medication cycles of conception or in the previous medication cycles depending on the date of conception:
 - not all active tablets are taken (based on returned medication, recordings in the e-diary and non-compliance based on DRSP levels, if necessary)

- there is a tablet free interval between the previous medication cycle and the medication cycle of conception
- vomiting or diarrhea is documented
- administration of prohibited prior or concomitant therapy as detailed in Section 10.7 of the Clinical Trial Protocol is documented
- Pregnancy ratio in women aged ≤ 35 years (Life table analysis)

In addition to PI analysis, method failure life table analysis and life table analysis on evaluable cycles will be performed in women aged ≤ 35 years (at the time of trial enrollment) in order to have the pregnancy rate at each cycle and cumulative pregnancy rates for 6 and 13 cycles. For life table analysis on evaluable cycles, only medication cycles of non-breastfeeding women will be considered as evaluable as defined in 2.2.1 and will be included in analysis. If the cycle is not evaluable but the subject became pregnant in this cycle, the cycle has to be included in the analysis. All pregnancies following premature termination of IMP will not be included in calculations if they occur later than seven days after the last tablet intake (active or placebo). Method failure pregnancy rates similar to method failure PI will include only those cycles of women who use the IMP correctly and include only perfect medication cycles as described in Section 5.5 of non-breastfeeding women.

- Overall PI, PI for method failures, PI for evaluable cycles and pregnancy ratio (life table analysis) in all women

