2.6 Sample Size

At least 920 subjects will be allocated to treatment to have at least 5000 evaluable cycles for the PI calculation in non-breastfeeding women aged ≤ 35 years (at the time of trial enrollment). Additionally, a minimum of 75 subjects aged > 35 years will be allocated to treatment. The calculations are based on empirical values including firstly a rate of 24.8% of subjects using back-up contraception or not having intercourse. Secondly, 45% of subjects are assumed to drop out of the trial. The prime target is to collect at least 5000 evaluable cycles.

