3. ANALYSIS SETS AND SUBGROUPS

3.1 Analysis Sets

As described in the “CF111303: Site 104: Addendum to Investigation Report Signed 18-August-2016 by [name], SCOPE CRA Manager”, “CF111303: Site 120: Addendum to Serious Breach Reporting Form Signed 23-August-2016 by [name], SCOPE Project Manager” and sponsor letter “RE: Clinical Trial CF111-303: exclude data from analysis for sites 104 and site 120” data from sites 104 and 120 will not be included in any statistical summary or analysis tables. Data from these sites will only be included in the Appendix 4 tables (Tables 15.1.1.1.1, 15.1.2.1.1, 15.1.3.1.1, 15.2.1.2.5, 15.2.1.2.7, 15.2.1.4.3, 15.2.1.4.5, 15.2.1.4.7, 15.2.1.4.9, 15.2.3.1.1 and 15.2.3.1.2), Appendix 5 listings and Appendix 6 figures (Figures 15.1.1.1, 15.1.2.1).

The analyses will be based on the following analysis sets:

Enrolled Set (ES) will consist of all subjects who signed informed consent/assent.

Safety Set (SS) will consist of all subjects who:

- took at least one dose of IMP.

Full Analysis Set (FAS) will consist of all subjects who:

- took at least one dose of IMP;
- were not pregnant at the date of first IMP intake.

Modified Full Analysis Set (MFAS) will consist of all subjects who:

- took at least one dose of IMP;
- were not pregnant at the date of first IMP intake;
- were non-breastfeeding.

Per Protocol Set (PPS) will not be defined since PI will be calculated using three methods therefore protocol violations will be taken into account.

Data of centers 104 and 120 will be excluded for SS and FAS calculations. Data of these centers will also be excluded for MFAS calculations unless it will be specified in the header of the respective tables that data of these centers are included.

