3.3 Data Review

A data review meeting (DRM) will be held after database lock, prior to the final SAP and clinical database closure.

The following aims are defined for the DRM:

- to assign pregnancies to their category and cycle;
- to identify protocol deviations which may have impact on cycles;
- to assign subjects to each of the analysis sets;
- to check that there are no data issues that are outstanding or need resolution;
- to define complete and correct diary entry;
- to solve any outstanding issues in the SAP.

Appropriate trial team, including a physician, will review certain potential protocol deviations and will review relevant information regarding those deviations to determine whether each of them have an impact on a perfect cycle. Protocol deviations will be not categorized into major and minor rather they will be categorized according to their impact to the perfect medication cycle.

Inclusion criterion related deviations will be classified as follows:

Inclusion criteria (At Visit 1 (Screening) and at Visit 1b (Medication Dispensation), subjects must meet ALL of the following criteria)	Impact on the cycle	DRM listing no.

1. Sexually active, postmenarcheal and premenopausal female subjects at risk of pregnancy with no upper age limit.
 
Since Protocol Final Version 4.0: Sexually active, postmenarcheal and premenopausal female subjects at risk of pregnancy including breastfeeding women with no upper age limit.
	Case by case decision	IN01, IN02

2. Female subjects at risk of pregnancy, between the ages of 15 and 17 (inclusive) provided that
 
 • Applicable national, state and local laws allow subjects in this age group to consent to receive contraceptive services, • All applicable laws and regulations regarding the informed consent of the subjects to participate in clinical trials are observed, and • Subjects in this age group will also be encouraged to consistently and correctly use male condoms with every event of sexual intercourse. 
Since Protocol Final Version 4.0: Female subjects at risk of pregnancy, between the ages of 15 and 17 (inclusive) provided that
 
 • Applicable national, state and local laws allow subjects in this age group to consent/assent to receive contraceptive services, and 	All cycles	IN03

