Method failure pregnancy*	All on-drug pregnancies of women who used the IMP correctly. Pregnancies are to be excluded from the calculation if in medication cycles of conception or in the previous medication cycles depending on the date of conception: 
 - not all active tablets are taken (based on returned medication, recordings in the e-diary and non-compliance based on DRSP levels, if necessary) - there is an active tablet free interval between the previous medication cycle and the medication cycle of conception. Tablet free interval will be determined by record from treatment diary. - vomiting or diarrhea is documented - administration of prohibited prior or concomitant therapy as detailed in Section 10.7 of the Clinical Trial Protocol is documented
Exposure cycles	28-day cycles, where at least one treatment diary entry of IMP intake is available. In addition, a cycle will be an exposure cycle if the subject become pregnant during this cycle regardless this cycle was a 28-day cycle or not.
Evaluable cycle	Cycles are exposure cycles with intercourse without back-up contraceptive at least once per cycle based on electronic diary question 'Did you have sexual

	
intercourse since the beginning of the cycle?" and answered with: 'Yes I had sexual intercourse without additional contraception'.
 
Also, cycle is to be defined as evaluable if:
 
 - Subject became pregnant at the respective cycle regardless back-up contraception was used or not. - Cycle has missing answer about intercourse or answered "I had NO sexual intercourse at all" but subject became pregnant at the respective cycle. 
Cycle will not be defined as evaluable if subject did not become pregnant and:
 
 - The question was answered with 'Yes I had sexual intercourse with additional contraception'. - Cycles with NO intercourse. - Cycle has missing answer about intercourse.
Perfect cycle*	
Evaluable cycles which have no:
 
 - >48h tablet free interval during the second IMP intake till day 24 of each cycle or >144h interval between the last IMP intake and the first IMP intake in consecutive cycles. Tablet free interval calculation will not take into account cycle days 25-28. - 4 or more days with forgotten tablets intake during 1-24 cycle days. - Protocol deviations having effect on this cycle.

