5.5.2 Secondary Efficacy Analysis

Secondary Efficacy Analysis will be based on non-breastfeeding women. Also, analysis will be performed in BMI subgroups.

Overall PI

Overall PI will be calculated based on exposure cycles for all women, aged ≤ 35 years and aged > 35 years:

$$PI \text{ (exposure cycles)} = \frac{\sum \text{on-drug pregnancy} \in \{\text{exposure cycles}\}}{\#\{\text{exposure cycles}\}} \times 1300.$$

Respective two-sided 95% CI for overall PI will be calculated according to formula in Section 5.5.

PI for method failures

PI for method failures will be calculated based on perfect cycles for all women, aged ≤ 35 years and aged > 35 years. Number of pregnancies will be calculated according to method failure definition:

$$PI (method failure) = \frac{\sum \text{method failure pregnancy} \in \{\text{perfect cycles}\}}{\#\{\text{perfect cycles}\}} \times 1300.$$

Respective two-sided 95% CI for PI for method failures will be calculated according to formula in Section 5.5.

Evaluable cycles PI

Evaluable cycles PI will be calculated based on evaluable cycles for all women and women aged > 35 years:

$$PI (\text{evaluable cycles}) = \frac{\sum \text{on-drug pregnancy} \in \{\text{evaluable cycles}\}}{\#\{\text{evaluable cycles}\}} \times 1300.$$

Respective two-sided 95% CI for PI based on evaluable cycles will be calculated according to formula in Section 5.5.

Life table analysis for pregnancy rate

Method failure life table analysis and life table analysis on evaluable cycles will be performed in all women, women aged ≤ 35 and > 35 years in order to have the pregnancy rate at each cycle and cumulative pregnancy rates for 6 and 13 cycles.

Cumulative pregnancy rate will be calculated by using the **PROC LIFETEST** procedure:

```
PROC LIFETEST DATA=<data set> METHOD=KM OUTSURV=CL CONFTYPE=LOG;
      TIME <time variable>*<censorship flag>(1);
      RUN;
```

The Kaplan-Meier method will be used to estimate the cumulative pregnancy ratio. Logarithmic transformation will be used for 95% CI of the pregnancy rate. The period from the start of treatment until the pregnancy will be the time variable in this analysis. Subjects who did not become pregnant will be censored at their time of the last intake of IMP.

Tables

No.	Name	Analysis set	Comments

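### The life-table time rule in SAP 5.5.2 keeps non-qualifying cycles at risk, so the evaluable-cycle and method-failure tables understate the rates that SAP 2.2.2 defines

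*SAP*

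**What the plan says.** SAP 2.2.2 defines which cycles count. For the first restricted table: "For life table analysis on evaluable cycles, only medication cycles of non-breastfeeding women will be considered as evaluable as defined in 2.2.1", with a cycle kept if the woman conceived in it. For the method-failure table, the rates "include only perfect medication cycles as described in Section 5.5 of non-breastfeeding women".

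SAP 5.5.2 (Life table analysis for pregnancy rate) names these same two analyses and gives one time rule: "The period from the start of treatment until the pregnancy will be the time variable in this analysis". The censoring rule is: "Subjects who did not become pregnant will be censored at their time of the last intake of IMP". The Kaplan-Meier call takes one time and one censoring flag per record, with no entry time or gap.

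The table list in 5.5.2 has three separate families: overall (15.2.2.1.x), evaluable-cycle (15.2.2.2.x) and method-failure (15.2.2.3.x). All are run on the MFAS. SAP 3.1 defines that set by at least one dose, no pregnancy at first intake and not breastfeeding; it does not require an evaluable cycle.

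In the SAP 5.5 definitions a cycle is evaluable whenever "Subject became pregnant at the respective cycle regardless back-up contraception was used or not". A footnote there confines method-failure pregnancies to perfect cycles.

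**The concern.** A clock that runs from first intake to pregnancy or last intake includes every cycle in between. A cycle with no intercourse, with back-up contraception or with missed tablets stays in the denominator, although 2.2.2 says it should not be there. Deleting the rows for such cycles changes nothing, because neither the start nor the end date moves. The MFAS does not remove them either.

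For the evaluable-cycle tables the events are the same as in the overall tables, since every on-drug pregnancy cycle is evaluable by definition. Same events and same clock give essentially the same table, except for any women with no evaluable cycle whom a programmer decides to leave out.

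For the method-failure tables, a pregnancy in an imperfect cycle is not an event, yet the imperfect cycles remain at risk. The censoring rule covers only women who did not become pregnant, so 5.5.2 also leaves open when a woman with a non-method-failure pregnancy leaves the risk set.

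The result would be two table families with a cycle-restricted title over a rate computed on all treatment time. The evaluable-cycle cumulative rate would not agree with the evaluable-cycle Pearl Index reported beside it.

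**Working it through.** **Inputs from the documents.** 13 cycles; reporting at 6 and 13 cycles; 920 women aged 35 or under; 45% dropout; and "a rate of 24.8% of subjects using back-up contraception or not having intercourse" (SAP 2.6).

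**Assumed.** The 24.8% is stated for subjects and is applied here to cycles, so the evaluable share is q = 0.752. The documents give neither a Pearl Index (PI) nor a perfect-cycle share, so ranges are used.

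**1. The plan's own figure.** 920 × 13 × 0.752 × 0.55 = 4,947 evaluable cycles; 5,000 would need 5,000 / (13 × 0.752 × 0.55) = 930 women. This reproduces the planning figure to about 1%. It does not show whether the 24.8% falls on the same women throughout or varies from cycle to cycle.

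**2. Direction.** The cumulative rate is 1 − Π(1 − d_k/n_k). In the evaluable-cycle table d_k is the same under both sections. Under 5.5.2, n_k is all women on treatment; under 2.2.2 it is only those whose cycle k qualifies. The first is never smaller, so the 5.5.2 rate is lower, or equal if no non-qualifying cycle is at risk. This needs none of the assumed inputs. For method failure the same argument holds once events are limited to perfect-cycle pregnancies, as the 5.5 footnote requires.

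**3. Size, evaluable-cycle tables.** As written: 1 − (1 − q·PI/1300)^k. As defined in 2.2.2: 1 − (1 − PI/1300)^k.

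| Assumed PI | 6 cycles, as written | 6 cycles, as defined | 13 cycles, as written | 13 cycles, as defined |
|---|---|---|---|---|
| 2 | 0.69% | 0.92% | 1.49% | 1.98% |
| 4 | 1.38% | 1.83% | 2.97% | 3.93% |
| 6 | 2.06% | 2.74% | 4.42% | 5.84% |

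The ratio is about 0.75. With 10% or 35% of cycles non-evaluable and PI 4, the 13-cycle figure as written is 3.54% or 2.57%, against 3.93%. On expected counts (920 women, 55% starting cycle 13), the log-transformed 95% CI at PI 4 is 1.67–4.24% as written and 2.22–5.60% as defined.

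**4. Clustering.** Non-evaluable cycles may concentrate in some women. Simulated 13-cycle rates (920 women, 55% starting cycle 13, PI 4, evaluability varying between women with mean 0.752, 3,000 replicates):

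| Within-woman correlation | MFAS as written | Dropping women with no evaluable cycle | Cycle-restricted |
|---|---|---|---|
| 0 | 2.98% | 2.99% | 3.95% |
| 0.2 | 2.94% | 2.95% | 3.89% |
| 0.5 | 2.96% | 3.10% | 3.92% |
| 0.8 | 2.97% | 3.49% | 3.94% |
| 1 | 2.97% | 3.95% | 3.95% |

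On the MFAS the shortfall stays at 24–25% whatever the clustering. It disappears only if all non-evaluable cycles fall in the same women and those women are dropped, which the SAP does not say.

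**5. Method-failure tables.** Assume a perfect-cycle PI of 2 and 60–80% of evaluable cycles perfect, so 0.752 × 0.6 = 45% to 0.752 × 0.8 = 60% of all cycles. At 13 cycles the rate is 0.90–1.20% as written against 1.98%; at 6 cycles, 0.42–0.55% against 0.92%. The unstated censoring time for imperfect-cycle pregnancies matters little. Censoring at the pregnancy, rather than keeping the woman at risk to cycle 13, moves the 13-cycle rate by at most about 0.01 percentage point (0.899% against 0.886% at the extreme, imperfect-cycle PI 8).

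**The case against.** The strongest reply is that this is under-specification, not a wrong estimator. SAP 2.2.2 states the restriction, 5.5.2 calls the analysis a life table on evaluable cycles, and the data set, time variable and flag in the code are placeholders. A programmer could honour 2.2.2, and three near-duplicate families are unlikely to have been intended. That is fair about intent. But 5.5.2 does fix the time variable and the censoring time in words, and those words conflict with 2.2.2. A programmer who departs from them could use cycle-specific risk sets, a clock that counts evaluable cycles only, or exclusion of women with no evaluable cycle, and these need not agree.

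Other points stand in part:

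- 5.5.2 ties the procedure to the cumulative rate and gives no formula for the per-cycle rate, so that column might be built correctly. The cumulative rates at 6 and 13 cycles would still be wrong.
- The direction for method failure depends on flagging only perfect-cycle pregnancies. If every pregnancy were flagged, the rate could be overstated. The 5.5 footnote rules that out, but 5.5.2 does not define the flag.
- The SAP lists an appendix of table specifications whose content is not in the text available. Nothing visible repairs the rule.
- With few events the log-transformed limits can fall below zero. The prespecified interval already has this feature; truncation at zero handles it.
- The life tables are descriptive, no threshold is attached to them in the available text, and correctly denominated Pearl Indices are reported as well. That limits the severity but does not remove the error.

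**Conclusion.** The concern holds. As written, 5.5.2 does not deliver the cycle-restricted rates of 2.2.2, and both restricted families come out too low. For the evaluable-cycle tables the direction follows from the definitions alone; for method failure it also uses the footnote that limits the events.

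The size is conditional. If the 24.8% planning rate applies per cycle, the evaluable-cycle rates are about 25% too low in relative terms, or 10% to 35% too low over the same range of non-evaluable cycles. The method-failure rates would be roughly 40% to 55% too low under the assumed perfect-cycle shares (1.20/1.98 = 0.61; 0.90/1.98 = 0.45).

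The primary and secondary Pearl Indices name their own cycle denominators and are not affected. The rule should be corrected, but it does not threaten the primary analysis.

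**What to change.** In SAP 5.5.2, for Tables 15.2.2.2.x and 15.2.2.3.x:

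- Let n_k be the women who contribute an evaluable (or perfect) cycle k, and d_k the on-drug (or method-failure) pregnancies conceived in that cycle.
- Report d_k/n_k for each cycle and 1 − Π(1 − d_k/n_k) through cycles 6 and 13.
- Keep the log-transformed 95% CI: limits for survival of S·exp(±1.96·√Σ d_k/[n_k(n_k − d_k)]), each subtracted from 1, with a lower limit below zero set to zero.
- In the method-failure tables, flag only method-failure pregnancies as events and censor a woman with any other pregnancy at that cycle.
- Keep the treatment-time Kaplan-Meier for the overall tables (15.2.2.1.x) only.

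Re-indexing by cumulative evaluable cycle would also honour 2.2.2. The calendar-cycle form is suggested because the tables promise a rate at each cycle.

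The cost is SAP wording and some reprogramming. No new data are needed: the cycle flags are already derived for the Pearl Indices, and the data review meeting is already charged "to assign pregnancies to their category and cycle". The reported rates will rise (2.97% to 3.93% in the PI 4 example), and n_k will vary by cycle, which needs a footnote. Support at cycle 13 remains adequate on planning figures: 920 × 0.55 = 506 completers, of whom about 506 × 0.752 = 381 have an evaluable cycle 13 and 228–304 (60–80% of those) a perfect one, before pregnancies.

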5.6 Safety Analysis

Analysis of safety endpoints will be conducted using the SS only.

5.6.1 Adverse Events

AE data includes:

- AE ID number
- AE name
- Start date
- Stop date
- Severity (mild, moderate, severe)
- Outcome (recovered/resolved, recovered/resolved with sequelae, not recovered/not resolved, recovering/resolving, fatal, unknown)
- Action taken with IMP (dose not changed, drug interrupted, drug withdrawn, not applicable, unknown)
- Relationship to IMP (unrelated, unlikely, possible, probable, definite)
- Other actions (none, medication required, tests required, hospitalization required or prolonged, other)
- Serious (yes, no)

The maximum severity (intensity) of the AE will be categorized by the investigator as follows:

- **Mild:** a type of AE that is usually transient and may require only minimal treatment or therapeutic intervention. The event does not generally interfere with usual activities of daily living.
- **Moderate:** a type of AE that is usually alleviated with additional specific therapeutic intervention. The event interferes with usual activities of daily living, causing discomfort but poses no significant or permanent risk of harm to the research participant.
- **Severe:** a type of AE that requires intensive therapeutic intervention. The event interrupts usual activities of daily living, or significantly affects clinical status. The event possesses a significant risk of harm to the research participant and hospitalization may be required.

AEs severity will be defined as “Unknown” if severity assessment is missing.

Drug relationship of adverse events

The relationship of an AE to the IMP is a clinical decision by the investigator based on all available information and is graded as follows:

- **Unrelated:** A clinical event with no evidence of any causal relationship.
- **Unlikely:** A clinical event, including laboratory test abnormality, with a temporal relationship to drug administration which makes a causal relationship improbable, and in which other drugs, chemicals or underlying disease provide plausible explanations.
- **Possible:** A clinical event, including laboratory test abnormality, with a reasonable time sequence to administration of the drug, but which could also be explained by concurrent disease or other drugs or chemicals. Information on drug withdrawal may be lacking or unclear.
- **Probable:** A clinical event, including laboratory test abnormality, with a reasonable time sequence to administration of the drug, unlikely to be attributed to concurrent disease or other drugs or chemicals, and which follows a clinically reasonable response on withdrawal (dechallenge). Rechallenge information is not required to fulfil this definition.
- **Definite:** A clinical event, including laboratory test abnormality, occurring in a plausible time relationship to drug administration, and which cannot be explained by concurrent disease or other drugs or chemicals. The response to withdrawal of the drug (dechallenge) should be clinically

plausible. The event must be definitive pharmacologically or phenomenologically, using a satisfactory rechallenge procedure if necessary.

Related AEs include the categories “possible”, “probable” and “definite”.

Unrelated AEs include the categories “unrelated” and “unlikely”.

The relationship of an AE to the IMP will be defined as “Unknown” if relationship grade assessment is missing.

Treatment Emergent Adverse Events

An AE that emerges during treatment having been absent prior to treatment or worsens relative to the pre-treatment state is defined as treatment emergent adverse event (TEAE). All AEs with onset or worsening after first intake of IMP until 10 days after last intake of IMP are defined as treatment emergent.

Where only partial dates are present, the month and/or year may be sufficient alone for assignment of treatment emergent AEs but in cases where this is not possible these AEs will be considered as treatment emergent.

Serious Adverse Events

An AE or suspected adverse reaction is considered “serious” if, in the view of either the investigator or sponsor, it results in any of the following outcomes:

- Death
- A life-threatening
- Inpatient hospitalization or prolongation of existing hospitalization
- A persistent or significant incapacity or substantial disruption of the ability to conduct normal life functions
- Congenital anomaly/birth defect

Adverse Events of Special Interest

Adverse events of special interest will be defined as hyperkalemia and venous thromboembolism events. Hyperkalemia will be identified as AEs with preferred terms “Hyperkalaemia” and “Blood potassium increased”. Venous thromboembolism will be identified as embolic and thrombotic venous events and assignments will be handled by Medical Monitors after database closure.

Adverse events leading to trial termination

Defined as those events where “Action taken with investigational medicinal product” is indicated as “drug withdrawn”.

All AEs will be summarized by calculating the number and percent of subjects with AEs as well as number of events. TEAEs will be summarized by calculating the number and percent of subjects with AEs by preferred term and system organ class. Also, TEAEs will be summarized by severity and relationship to treatment. Number and percent of subjects with serious TEAEs, TEAEs leading to trial termination and TEAEs of special interest will be provided by MedDRA PT and SOC.

Summaries of AEs will be repeated for defined subgroups.

Tables

No.	Name	Analysis set	Comments
Table 15.3.1.1.1	Summary of Adverse Events	Safety	An overall summary of AEs will be provided for subjects in the SS. Percentage will be based on SS. Data of centers 104 and 120 will be excluded.
Table 15.3.1.1.2	Summary of Adverse Events by Weight Subgroup	Safety	An overall summary of AEs will be provided for subjects in the SS. Percentage will be based on SS. Data of centers 104 and 120 will be excluded.

Table 15.3.1.1.3	Summary of Adverse Events by BMI Subgroup	Safety	An overall summary of AEs will be provided for subjects in the SS. Percentage will be based on SS. Data of centers 104 and 120 will be excluded.
Table 15.3.1.1.4	Summary of Adverse Events by Blood Pressure Subgroup	Safety	An overall summary of AEs will be provided for subjects in the SS. Percentage will be based on SS. Data of centers 104 and 120 will be excluded.
Table 15.3.1.1.5	Summary of Adverse Events by Race Subgroup	Safety	An overall summary of AEs will be provided for subjects in the SS. Percentage will be based on SS. Data of centers 104 and 120 will be excluded.
Table 15.3.1.1.6	Summary of Adverse Events by Ethnicity Subgroup	Safety	An overall summary of AEs will be provided for subjects in the SS. Percentage will be based on SS. Data of centers 104 and 120 will be excluded.
Table 15.3.1.2.1	Incidence of TEAEs	Safety	The number and percentage of subjects reporting TEAEs will be summarized by PT nested within SOC. Percentage will be based on SS. Data of centers 104 and 120 will be excluded.
Table 15.3.1.2.2	Incidence of TEAEs by Weight Subgroup	Safety	The number and percentage of subjects reporting TEAEs will be summarized by PT nested within SOC. Percentage will be based on SS. Data of centers 104 and 120 will be excluded.
Table 15.3.1.2.3	Incidence of TEAEs by BMI Subgroup	Safety	The number and percentage of subjects reporting TEAEs will be summarized by PT nested within SOC. Percentage will be based on SS. Data of centers 104 and 120 will be excluded.
Table 15.3.1.2.4	Incidence of TEAEs by Blood Pressure Subgroup	Safety	The number and percentage of subjects reporting TEAEs will be summarized by PT nested within SOC. Percentage will be based on SS. Data of centers 104 and 120 will be excluded.
Table 15.3.1.2.5	Incidence of TEAEs by Race Subgroup	Safety	The number and percentage of subjects reporting TEAEs will be summarized by PT nested within SOC. Percentage will be based on SS. Data of centers 104 and 120 will be excluded.
Table 15.3.1.2.6	Incidence of TEAEs by Ethnicity Subgroup	Safety	The number and percentage of subjects reporting TEAEs will be summarized by PT nested within SOC. Percentage will be based on SS. Data of centers 104 and 120 will be excluded.
Table 15.3.1.3.1	Incidence of TEAEs by Relationship	Safety	The number and percentage of subjects reporting TEAEs by relationship to study medication will be summarized by PT nested within SOC. Percentage will be based on SS. Data of centers 104 and 120 will be excluded.
Table 15.3.1.3.2	Incidence of TEAEs by Relationship by Weight Subgroup	Safety	The number and percentage of subjects reporting TEAEs by relationship to study medication will be summarized by PT nested within SOC. Percentage will be based on SS. Data of centers 104 and 120 will be excluded.
Table 15.3.1.3.3	Incidence of TEAEs by Relationship by BMI Subgroup	Safety	The number and percentage of subjects reporting TEAEs by relationship to study medication will be summarized by PT nested within SOC. Percentage will be based on SS. Data of centers 104 and 120 will be excluded.
Table 15.3.1.3.4	Incidence of TEAEs by Relationship by Blood Pressure Subgroup	Safety	The number and percentage of subjects reporting TEAEs by relationship to study medication will be summarized by PT nested within SOC. Percentage will be based on SS. Data of centers 104 and 120 will be excluded.
Table 15.3.1.3.5	Incidence of TEAEs by Relationship by Race Subgroup	Safety	The number and percentage of subjects reporting TEAEs by relationship to study medication will be summarized by PT nested within SOC. Percentage will be based on SS. Data of centers 104 and 120 will be excluded.
Table 15.3.1.3.6	Incidence of TEAEs by Relationship by Ethnicity Subgroup	Safety	The number and percentage of subjects reporting TEAEs by relationship to study medication will be summarized by PT nested within SOC. Percentage will be based on SS. Data of centers 104 and 120 will be excluded.
Table 15.3.1.4.1	Incidence of TEAEs by Worst Severity	Safety	The number and percentage of subjects reporting TEAEs by worst severity will be summarized by PT nested within SOC. Percentage will be based on SS. Data of centers 104 and 120 will be excluded.
Table 15.3.1.4.2	Incidence of TEAEs by Worst Severity by Weight Subgroup	Safety	The number and percentage of subjects reporting TEAEs by worst severity will be summarized by PT nested within SOC. Percentage will be based on SS. Data of centers 104 and 120 will be excluded.

Table 15.3.1.4.3	Incidence of TEAEs by Worst Severity by BMI Subgroup	Safety	The number and percentage of subjects reporting TEAEs by worst severity will be summarized by PT nested within SOC. Percentage will be based on SS. Data of centers 104 and 120 will be excluded.
Table 15.3.1.4.4	Incidence of TEAEs by Worst Severity by Blood Pressure Subgroup	Safety	The number and percentage of subjects reporting TEAEs by worst severity will be summarized by PT nested within SOC. Percentage will be based on SS. Data of centers 104 and 120 will be excluded.
Table 15.3.1.4.5	Incidence of TEAEs by Worst Severity by Race Subgroup	Safety	The number and percentage of subjects reporting TEAEs by worst severity will be summarized by PT nested within SOC. Percentage will be based on SS. Data of centers 104 and 120 will be excluded.
Table 15.3.1.4.6	Incidence of TEAEs by Worst Severity by Ethnicity Subgroup	Safety	The number and percentage of subjects reporting TEAEs by worst severity will be summarized by PT nested within SOC. Percentage will be based on SS. Data of centers 104 and 120 will be excluded.
Table 15.3.1.5.1	Incidence of Serious TEAEs	Safety	The number and percentage of subjects reporting serious TEAEs will be summarized by PT nested within SOC. Percentage will be based on SS. Data of centers 104 and 120 will be excluded.
Table 15.3.1.5.2	Incidence of Serious TEAEs by Weight Subgroup	Safety	The number and percentage of subjects reporting serious TEAEs will be summarized by PT nested within SOC. Percentage will be based on SS. Data of centers 104 and 120 will be excluded.
Table 15.3.1.5.3	Incidence of Serious TEAEs by BMI Subgroup	Safety	The number and percentage of subjects reporting serious TEAEs will be summarized by PT nested within SOC. Percentage will be based on SS. Data of centers 104 and 120 will be excluded.
Table 15.3.1.5.4	Incidence of Serious TEAEs by Blood Pressure Subgroup	Safety	The number and percentage of subjects reporting serious TEAEs will be summarized by PT nested within SOC. Percentage will be based on SS. Data of centers 104 and 120 will be excluded.
Table 15.3.1.5.5	Incidence of Serious TEAEs by Race Subgroup	Safety	The number and percentage of subjects reporting serious TEAEs will be summarized by PT nested within SOC. Percentage will be based on SS. Data of centers 104 and 120 will be excluded.
Table 15.3.1.5.6	Incidence of Serious TEAEs by Ethnicity Subgroup	Safety	The number and percentage of subjects reporting serious TEAEs will be summarized by PT nested within SOC. Percentage will be based on SS. Data of centers 104 and 120 will be excluded.
Table 15.3.1.6.1	Incidence of TEAEs Leading to Trial Termination	Safety	The number and percentage subjects reporting TEAEs leading to trial termination will be summarized by PT nested within SOC. Percentage will be based on SS. Data of centers 104 and 120 will be excluded.
Table 15.3.1.6.2	Incidence of TEAEs Leading to Trial Termination by Weight Subgroup	Safety	The number and percentage of subjects reporting TEAEs leading to trial termination will be summarized by PT nested within SOC. Percentage will be based on SS. Data of centers 104 and 120 will be excluded.
Table 15.3.1.6.3	Incidence of TEAEs Leading to Trial Termination by BMI Subgroup	Safety	The number and percentage of subjects reporting TEAEs leading to trial termination will be summarized by PT nested within SOC. Percentage will be based on SS. Data of centers 104 and 120 will be excluded.
Table 15.3.1.6.4	Incidence of TEAEs Leading to Trial Termination by Blood Pressure Subgroup	Safety	The number and percentage of subjects reporting TEAEs leading to trial termination will be summarized by PT nested within SOC. Percentage will be based on SS. Data of centers 104 and 120 will be excluded.
Table 15.3.1.6.5	Incidence of TEAEs Leading to Trial Termination by Race Subgroup	Safety	The number and percentage of subjects reporting TEAEs leading to trial termination will be summarized by PT nested within SOC. Percentage will be based on SS. Data of centers 104 and 120 will be excluded.
Table 15.3.1.6.6	Incidence of TEAEs Leading to Trial Termination by Ethnicity Subgroup	Safety	The number and percentage of subjects reporting TEAEs leading to trial termination will be summarized by PT nested within SOC. Percentage will be based on SS. Data of centers 104 and 120 will be excluded.
Table 15.3.1.7.1	Incidence of TEAEs of Special Interest	Safety	The number and percentage of subjects reporting TEAEs of special interest will be summarized by PT nested within SOC. Percentage will be based on SS. Data of centers 104 and 120 will be excluded.

Table 15.3.1.7.2	Incidence of TEAEs of Special Interest by Weight Subgroup	Safety	The number and percentage of subjects reporting TEAEs of special interest will be summarized by PT nested within SOC. Percentage will be based on SS. Data of centers 104 and 120 will be excluded.
Table 15.3.1.7.3	Incidence of TEAEs of Special Interest by BMI Subgroup	Safety	The number and percentage of subjects reporting TEAEs of special interest will be summarized by PT nested within SOC. Percentage will be based on SS. Data of centers 104 and 120 will be excluded.
Table 15.3.1.7.4	Incidence of TEAEs of Special Interest by Blood Pressure Subgroup	Safety	The number and percentage of subjects reporting TEAEs of special interest will be summarized by PT nested within SOC. Percentage will be based on SS. Data of centers 104 and 120 will be excluded.
Table 15.3.1.7.5	Incidence of TEAEs of Special Interest by Race Subgroup	Safety	The number and percentage of subjects reporting TEAEs of special interest will be summarized by PT nested within SOC. Percentage will be based on SS. Data of centers 104 and 120 will be excluded.
Table 15.3.1.7.6	Incidence of TEAEs of Special Interest by Ethnicity Subgroup	Safety	The number and percentage of subjects reporting TEAEs of special interest will be summarized by PT nested within SOC. Percentage will be based on SS. Data of centers 104 and 120 will be excluded.
Table 15.3.1.8.1	Incidence of Related Serious TEAEs	Safety	The number and percentage of subjects reporting related serious TEAEs will be summarized by PT nested within SOC. Percentage will be based on SS. Data of centers 104 and 120 will be excluded.
Table 15.3.1.8.2	Incidence of Related Serious TEAEs by Weight Subgroup	Safety	The number and percentage of subjects reporting related serious TEAEs will be summarized by PT nested within SOC. Percentage will be based on SS. Data of centers 104 and 120 will be excluded.
